## 6.2 PROCEDURES FOR ASSESSING EFFICACY

The efficacy of cART will be determined using viral load assays obtained at the local laboratories. In particular participants must have a plasma HIV RNA <50 copies/mL (<200 copies/mL if Taqman 2.0 Roche testing platform used) to be eligible for randomisation, either at week 22 (or any necessary repeat visits) or – for Cohort II – at screening. Any evidence of viral rebound during the study must be managed in accordance with standard national treatment guidelines.

## 6.3 PROCEDURES FOR ASSESSING SAFETY

All standard routine toxicity testing for cART, vaccine and vorinostat will be made according to the study visits. In addition, in the event of any abnormal blood test results these will be followed up with good clinical practice accordingly. Specific monitoring of the following parameters i.e. FBC, renal function (eGFR and uPCR), electrolytes i.e. calcium, magnesium and potassium; LFTs and blood

glucose will be conducted at specific time points in the study commensurate with the vorinostat dosing schedule Arm B.

Adverse events will be reported on the case report form. Adverse events (clinical and laboratory) will be graded using the 2004 (amended 2009) Division of AIDS toxicity grading table (see [Appendix III](#)). Serious adverse events will be defined according to principles of GCP, and should be reported to the CTU within 24 hours of the site being aware (see [Section 7](#)). All adverse events, after randomisation, meeting the definitions above should be reported on study CRFs, regardless of their relationship to HIV. Prior to randomisation only grade 3 and 4 adverse events and Serious Adverse Events (SAE) are collected.

#### **6.4 PROCEDURES FOR ASSESSING QUALITY OF LIFE**

All participants will be asked to complete the EQ-5D-5L questionnaire at enrolment (visit only applicable to Cohort I – Recently diagnosed), randomisation, post-randomisation week 08 day 3 (PR08-3) and the final visit, post-randomisation week 18 (PR18). ([Appendix X](#)).

#### **6.5 EARLY STOPPING OF FOLLOW-UP**

If a participant chooses to discontinue their study treatment, they should always be followed up providing they are willing, that is, they should be encouraged to not leave the whole study; if they do not wish to remain on study follow-up, however, their decision must be respected and the participant will be withdrawn from the study completely. The RIVER Co-ordinating Centre should be informed of this in writing using the appropriate documentation. Participants withdrawing completely have a negative impact on a study's data.

If the medical data collected during the participant's participation in the study are kept for research and analysis purposes, they can be anonymised if necessary. Consent for future use of stored samples already collected can be refused when leaving the study early (but this should be discouraged and should follow a discussion).

All participants will be followed up in the long-term as part of the RIVER study (see [Section 6.9](#)), which may include flagging with the NHS Information Centre, ONS or similar approaches.

#### **6.6 PARTICIPANT TRANSFERS**

If a participant moves from the area, every effort should be made for the participant to be seen at another participating study site. A copy of the participant's CRFs should be provided to the new site and the participant will need to sign a new consent form. Once this has been done, the new site will take over responsibility for the participant; until this has been done, responsibility for the participant lies with the original site.

#### **6.7 LOSS TO FOLLOW-UP**

In the statistical analysis, a patient will be classified as 'lost to follow-up' if they have not been seen in clinic for more than 3 months. For operational management, a patient will be classified as 'lost to

follow-up' (i.e no further efforts to trace the patient are being made) when they have missed 3 scheduled clinic visits and despite at least 3 documented attempts to contact them. Provided patients have consented to the site contacting their GP, the site will attempt to find further information on the patient's clinical status via the GP. Subsequently, if the patient attends clinic and a CRF is received by the RIVER Co-ordinating Centre, the 'lost to follow-up' status will be reversed.

## 6.8 ASSESSMENTS AT TRIAL CLOSURE

At the final study visit (PR18) all blood assessments will be taken for the final study end point. The participant will then continue with ART triple therapy and return to standard clinical care in consultation with their doctor.

## 6.9 LONG-TERM FOLLOW-UP

All participants will be followed-up annually for 5 years following the end of the interventional phase of the study.

To gather specific safety information specifically in regards to vorinostat – as the mechanism of action of vorinostat is gene modification this may carry unforeseen long-term consequences beyond the timeframe of the main study. Specific questions asked will include:

1. Safety related
  - Any new or exacerbation of haematological conditions including lab abnormalities.
  - Any new malignancies or pre-malignancies including skin cancers, anal intraepithelial neoplasia (AIN), cervical intraepithelial neoplasia (CIN), Barrett's oesophagus etc.
  - Any new or exacerbation of pre-existing medical problems.
  - Outcome of any pregnancies in female partners.
2. To gather HIV related information:
  - Antiretroviral drug use.
  - T-cells and viral load.
  - AIDS-defining illness (ADI) or serious non-AIDS (SNA) events.
3. To obtain longer-term follow up on impact of the intervention on measures of viral reservoir beyond the scope of the current research study a 40mL blood draw for HIV reservoir assessment (DNA) and gene transcription studies will be collected at each annual visit.

## 7 SAFETY REPORTING

The principles of GCP require that both investigators and sponsors follow specific procedures when notifying and reporting adverse events or reactions in clinical studies. These procedures are described in this section of the protocol. **Section 7.1** lists definitions, **Section 7.3** gives details of the investigator responsibilities and **Section 7.4** provides information on the RIVER Co-ordinating Centre responsibilities.

### 7.1 DEFINITIONS

The definitions of the EU Directive 2001/20/EC Article 2 based on the principles of GCP apply to this study protocol. These definitions are given in **Table 6**.

**Table 6 Definitions**

TERM	DEFINITION
Adverse Event (AE)	Any untoward medical occurrence in a participant or clinical study subject to whom a medicinal product has been administered including occurrences that are not necessarily caused by or related to that product.
Adverse Reaction (AR)	Any untoward and unintended response to an investigational medicinal product related to any dose administered.
Unexpected Adverse Reaction (UAR)	An adverse reaction, the nature or severity of which is not consistent with the information about the medicinal product in question set out in the Summary of Product Characteristics (SmPC) or Investigator Brochure (IB) for that product.
Serious Adverse Event (SAE) or Serious Adverse Reaction (SAR) or Suspected Unexpected Serious Adverse Reaction (SUSAR)	Respectively any adverse event, adverse reaction or unexpected adverse reaction that: 
 
▪ Results in death
 
▪ Is life-threatening+++
 
▪ Requires hospitalisation or prolongation of existing hospitalisation§§§
 
▪ Results in persistent or significant disability or incapacity
 
▪ Consists of a congenital anomaly or birth defect
 
▪ Is another important medical condition****
 

+++ The term life-threatening in the definition of a serious event refers to an event in which the participant is at risk of death at the time of the event; it does not refer to an event that hypothetically might cause death if it were more severe, for example, a silent myocardial infarction.

§§§ Hospitalisation is defined as an inpatient admission, regardless of length of stay, even if the hospitalisation is a precautionary measure for continued observation. Hospitalisations for a pre-existing condition, that has not worsened or for an elective procedure do not constitute an SAE.

\*\*\*\* Medical judgement should be exercised in deciding whether an AE or AR is serious in other situations. The following should also be considered serious: important AEs or ARs that are not immediately life-threatening or do not result in death or hospitalisation but may jeopardise the subject or may require intervention to prevent one of the other outcomes listed in the definition above; for example, a secondary malignancy, an allergic bronchospasm requiring intensive emergency treatment, seizures or blood dyscrasias that do not result in hospitalisation or development of drug dependency.

### 7.1.1 MEDICINAL PRODUCTS

An investigational medicinal product is defined as the tested investigational medicinal product and the comparators used in the study. (EU guidance ENTR/CT 3, April 2006 revision). In the RIVER study this includes:

- Vorinostat
- Raltegravir
- Combination ART backbone treatment
- ChAdV63.HIVconsv.
- MVA.HIVconsv vaccine

### 7.1.2 ADVERSE EVENTS

Adverse Events include:

- An exacerbation of a pre-existing illness.
- An increase in frequency or intensity of a pre-existing episodic event or condition.
- A condition (even though it may have been present prior to the start of the study) detected after study drug administration.
- Continuous persistent disease or a symptom present at baseline that worsens following administration of the study treatment.

Adverse Events do not include:

- Medical or surgical procedures; the condition that leads to the procedure is the adverse event.
- Pre-existing disease or a condition present before treatment that does not worsen.
- Hospitalisations where no untoward or unintended response has occurred, e.g., elective cosmetic surgery, social admissions.
- Accidental overdose of medication without signs or symptoms.

### 7.1.3 DISEASE-RELATED EVENTS

All adverse events meeting the definitions above, regardless of their relationship to HIV and should be graded (see [Appendix III](#)). For AE reporting requirements refer to [Section 7.4](#).

In particular, all deaths should be reported as fatal SAEs.

## 7.2 OTHER STUDY-SPECIFIC REQUIREMENTS & EXPLORATORY OUTCOMES

### 7.2.1 LARGE VOLUME BLOOD DRAW

The total blood draw over the study for both cohorts is approximately 1500 ml. The largest blood draws occur at randomisation (390ml) and post-randomisation week 16, PR16 (387ml). The UK blood transfusion service ([www.blood.co.uk/giving-blood](http://www.blood.co.uk/giving-blood)) recommends the following in regards to donating blood:

1. Aged 17-65 years and generally in good health.
2. Male donors can donate 4 times in a 12-month period, with each blood donation equal to 470 ml i.e. a total of 1880 ml/annum.
3. Female donors can donate 470mLs every 16 weeks, this is to reduce the risk of iron deficiency anaemia in those still menstruating.

4. Weight must be at least 50 kg, but in females under 20 years of age and weighing <65kg and less than 168cm in height, blood volume needs to be estimated before donation.

In the RIVER protocol, the risks of the blood draws are minimised through the following:

1. Haemoglobin (Hb) within the normal range and weight  $\geq 50$ kg as inclusion criteria for participation; women of CBP are excluded from participation, and none of the women included will be menstruating.
2. Cohort I – Recently diagnosed participants have primary HIV infection and it is most unlikely that there will be any impact on the haematological axis in such participants.
3. Hb checks prior to the larger volume blood draws at randomisation and PR16 i.e. at week 22/screening and PR12 respectively.
4. Participants in Cohort II – Previously diagnosed are excluded if in the 3 months prior to screening  $\geq 40$ ml of blood has been taken.
5. Sites are advised that the participant should not have any large blood draws for 3 months after the last study visit, PR18.

### 7.2.2 EXPLORATORY OUTCOMES – HUMAN ENDOGENOUS RETROVIRUSES

Some human endogenous retroviruses (HERVs) types have been associated with disease states including lymphoma and multiple sclerosis but the exact role (if any) that HERVs play in their aetiology remains to be determined. The effect of vorinostat on human endogenous retroviruses (HERVs) is unknown. Any elevation of HERVs that might occur as a consequence of exposure to vorinostat is unlikely to be sustained, as exposure to vorinostat is restricted to 10 doses only. Information on incident cancers including lymphoma will be collected for the duration of the study and 5 years after the interventional phase of the study (see [Section 6.9](#)). The levels of these viruses may be measured under two circumstances, first if an excess of malignancies in which HERVs could be plausibly be involved is seen; or second, as an additional exploratory analysis.

## 7.3 OTHER NOTABLE EVENTS

There are several other notable events which if they occur during the study should be recorded in the participant's medical notes and reported to the RIVER Co-ordinating Centre. Notable events may also be reportable as an SAE if any of the criteria listed in [Table 6](#) are met. Refer to [Appendix IV](#) for a full list of notable events.

### 7.3.1 VACCINE RELATED EVENTS

GSK, as owners of the ChAd vector, have a list of vaccine related adverse events which are of specific interest to them. Information on notable events will be collected on a study CRF, and further information on the event may be requested.

### 7.3.2 CANCERS

Despite the fact that vorinostat is an HDACi licensed in the USA for the treatment of cutaneous T-cell lymphoma and multiple myeloma, in regards to the non-clinical toxicology of the agent, carcinogenicity studies have not been performed. However, vorinostat is mutagenic in vitro in the bacterial reverse mutation assays causing chromosomal aberrations in vitro in Chinese hamster ovary and increased incidence of micro-nucleated erythrocytes when administered to mice (mouse micronucleus assay). The risk of malignancy in participants exposed to vorinostat, even for short periods, is unknown.

For this reason any diagnosis of cancer (or worsening cancer) throughout the study should be reported on a cancer specific study CRF.

Information on any new malignancies will also be collected during long-term follow up, where participants will be followed up annually for 5 years following the completion of the interventional phase of the study (see [Section 6.9](#)).

### 7.3.3 PREGNANCY

Women of child-bearing potential cannot participate in this study. In pre-clinical studies, there were chromosomal abnormalities induced by vorinostat in hamster ovary lines. It is unknown what impact, short exposure to vorinostat might have on the human ovary. Should the participant in the study father a child within 1 year of completing the course of vorinostat consent from the mother of the child will be sought to allow follow-up to the birth of the child.

Pregnancy in a partner should be reported as a notable event.

## 7.4 INVESTIGATOR RESPONSIBILITIES

All non-serious AEs and ARs, whether expected or not, should be recorded in the participant's medical notes and dependent on what stage of the study the participant has reached may need to be reported to the RIVER Co-ordinating Centre:

- Participants in Cohort I – Recently diagnosed will be on cART alone for 22 weeks prior to randomisation. During this period, prior to randomisation, only grade 3 and 4 adverse events need to be reported on study CRFs.
- From randomisation up until the participant's last study visit (PR18), in addition to grade 3 or 4 events, **all** non-serious AEs and ARs, whether expected or not, should also be recorded in the participant's medical notes and reported on the relevant study CRF.
- Adverse events should be sent to the RIVER Co-ordinating Centre within the agreed timescale of **7 days** from awareness of the event.
- SAEs, SARs and Notable Events should be notified to the RIVER Co-ordinating Centre within **24 hours** of the investigator becoming aware of the event.

### 7.4.1 INVESTIGATOR ASSESSMENT

#### 7.4.1.A SERIOUSNESS

When an AE or AR occurs, the investigator responsible for the care of the participant must first assess whether or not the event is serious using the definition given in [Section 7.1](#). If the event is serious, then an SAE Form must be completed and the RIVER Co-ordinating Centre notified within 24 hours.

#### 7.4.1.B SEVERITY OR GRADING OF ADVERSE EVENTS

The severity of all AEs and/or ARs (serious and non-serious) in this study should be graded using the toxicity grading table in [Appendix III](#).

#### 7.4.1.C CAUSALITY

The investigator must assess the causality of all serious events or reactions in relation to the study therapy using the definitions in [Table 7](#). There are five categories: unrelated, unlikely, possible, probable, and definitely related. If the causality assessment is unrelated or unlikely to be related, the

event is classified as an SAE. If the causality is assessed as possible, probable or definitely related, then the event is classified as an SAR.

If an SAE is considered to be related to study treatment and drug is stopped or the dose modified, refer to [Section 5.8](#).

**Table 7 Assigning Type of SAE Through Causality**

RELATIONSHIP	DESCRIPTION	SAE TYPE
Unrelated	There is no evidence of any causal relationship	Unrelated SAE
Unlikely	There is little evidence to suggest that there is a causal relationship (for example, the event did not occur within a reasonable time after administration of the study medication). There is another reasonable explanation for the event (for example, the participant's clinical condition, other concomitant treatment).	Unrelated SAE
Possible	There is some evidence to suggest a causal relationship (for example, because the event occurs within a reasonable time after administration of the study medication). However, the influence of other factors may have contributed to the event (for example, the participant's clinical condition or other concomitant treatments).	SAR
Probable	There is evidence to suggest a causal relationship and the influence of other factors is unlikely.	SAR
Definitely	There is clear evidence to suggest a causal relationship and other possible contributing factors can be ruled out.	SAR

#### 7.4.1.D EXPECTEDNESS

If there is at least a possible involvement of the study treatment (or comparator), the investigator must assess the expectedness of the event. An unexpected adverse reaction is one not previously reported in the current Summary of Product Characteristics (SmPC) or one that is more frequent or more severe than previously reported. The definition of an unexpected adverse reaction (UAR) is given in [Table 6](#). If a SAR is assessed as being unexpected, it becomes a SUSAR.

Please see [Appendix II](#) for details of expected toxicities associated with the drugs being used in this study.

#### 7.4.1.E NOTIFICATION

The RIVER Co-ordinating Centre should be notified by the investigator of all SAEs within **24 hours** of the investigator becoming aware of the event.

Investigators should notify the RIVER Co-ordinating Centre of any SAEs from the point the participant is recruited into the study. For Cohort I – Recently diagnosed participants investigators should notify the RIVER Co-ordinating Centre of any SAEs occurring from the time of enrolment until 12 weeks after the participant's last study visit (up until post-randomisation week 30). For Cohort II – Previously diagnosed participants investigators should notify the RIVER Co-ordinating Centre of any SAEs occurring from the time of randomisation until 12 weeks after the participant's last study visit

(up until post-randomisation week 30). Any subsequent events that may be attributed to treatment should be reported to the MHRA using the yellow card system.

Having reviewed and checked SAEs, the RIVER Co-ordinating Centre will then be responsible for reporting these to the sponsor within 7 days.

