Interventions to be Compared	This study is a two-arm prospective 1:1 randomised controlled trial comparing: Arm A: Combination ART (cART) preferably including raltegravir (control)* Arm B: Combination ART (cART) preferably including raltegravir* plus ChAdV63.HIVconsv (ChAd) prime and MVA.HIVconsv (MVA) boost vaccines; followed by a 28-day course of vorinostat (10 doses in total).
Study Hypothesis	In primary HIV infection, a combination of immediate cART, immunisation and latency reactivation using the HDACi vorinostat will confer a significant reduction in the HIV reservoir when compared with cART alone.
Primary Outcome Measure(s)	The primary study outcome measure is HIV 'total' DNA from CD4 T-cells.
Secondary Outcome Measure(s)	Secondary outcome measure include: 
 
▪ Clinical and laboratory adverse events, all grades, including SAE
 
▪ Further assessment of the HIV reservoir e.g. HIV integrated DNA; HIV cell associated RNA; plasma HIV RNA measured with an ultra-low copy assay i.e. with a threshold of <1 copy/ml, viral outgrowth assays
 
▪ Studies of immune function including measuring the latently-infected resting memory T-cells and cytotoxic immune responses
 
▪ Changes in inflammatory biomarkers
 

Randomisation	Participants will be randomised to either arm of the study in a 1:1 ratio once all inclusion criteria are met.
Duration	Planned duration 2.5 years. Participants will be followed for a minimum of 18 weeks after randomisation.
Sponsor	Imperial College London
Funder	Medical Research Council & industry partners
Legal Representative in Europe	Imperial College London
Chief Investigator	[name]
MRC CTU Project Leader	[name]

\* Preferred regimen prior to randomisation should contain raltegravir. However, where the use of raltegravir is contraindicated this can be substituted with another agent preferably in the same class. For some participants where this may require a switch prior to joining the study, the participant's regimen should be switched at least 6 weeks prior to randomisation. Any switch made specifically for entry into the study should be conducted after the participant has consented to join the study.

[figure not shown]

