### 5.2.3 USE OF ART PRIOR TO ENROLMENT – COHORT II – PREVIOUSLY DIAGNOSED

For previously diagnosed participants who have already started on ART (Cohort II) only those that started at least 3 drug ART at PHI diagnosis, have been on at least 3-drug ART for  $\geq 22$  weeks and  $\leq 2$  years and are still on ART at screening will be eligible for randomisation.

If a participant is already on combination ART regimen that includes raltegravir this participant can proceed straight to screening and randomisation.

The preferred regimen prior to randomisation should contain raltegravir. For those participants that are not on raltegravir, and are willing to switch regimen, we recommend that once consent for the study has been taken, their combination ART be changed 6 weeks prior to randomisation to include raltegravir. During these 6 weeks, any toxicities associated with this switch in regimen should be monitored as per routine clinical guidelines. If the new regimen is well tolerated and the participant is compliant with their new regimen they can proceed to screening and randomisation. The participant should then continue on raltegravir the duration of the study.

However, where the use of raltegravir is contraindicated this can be substituted with ideally another integrase inhibitor. If however it is not possible to substitute this and the participant is eligible for randomisation they can join the study on their current ART regimen.

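### Cohort II SAE notification opens at randomisation and so misses the six or more weeks after a switch to raltegravir made for study entry

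*Protocol*

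**What the plan says.** **When SAE notification starts.** Protocol 7.4.1.E opens with a general statement: "Investigators should notify the RIVER Co-ordinating Centre of any SAEs from the point the participant is recruited into the study". It then sets a start for each cohort. For Cohort I it is "any SAEs occurring from the time of enrolment until 12 weeks after the participant's last study visit". For Cohort II it is "any SAEs occurring from the time of randomisation until 12 weeks" after the last study visit. Both windows are stated to end at post-randomisation week 30.

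**When the ART change happens.** The Summary footnote asks for a change of regimen at least six weeks ahead of randomisation and adds: "Any switch made specifically for entry into the study should be conducted after the participant has consented to join the study". Section 5.2.3 recommends, for Cohort II participants who are not on raltegravir and are willing to change, that once consent has been taken "their combination ART be changed 6 weeks prior to randomisation to include raltegravir". It leaves toxicity in that period to routine clinical guidance, and lets the participant go on to screening and randomisation if the new regimen is well tolerated. Section 7.1.1 includes raltegravir in its list of investigational medicinal products.

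**What is collected before randomisation.** Section 6.3, repeated in SAP 2.3, says: "Prior to randomisation only grade 3 and 4 adverse events and Serious Adverse Events (SAE) are collected". Neither names a cohort. The corresponding bullet in section 7.4 describes pre-randomisation grade 3 and 4 reporting for Cohort I only.

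**The concern.** For a Cohort II participant who changes ART in order to join, study-related exposure to a listed investigational product begins before the reporting window opens. An untoward event after that change fits the adverse event definition in Protocol Table 6, but the cohort-specific sentence in 7.4.1.E does not ask the site to notify it.

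The gap is also selective. Tolerating the change is a condition for going forward, so those with the worst reactions are the least likely to be randomised. For them the trigger date never arrives. The co-ordinating centre's review of SAEs (section 7.5) starts from site reports, so an event that is not notified is not assessed centrally for causality or expectedness. The yellow card route in 7.4.1.E is for events after the window has closed, not before it opens.

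There is a smaller reporting consequence. SAP 4.8 presents pre-randomisation adverse events overall. If sites follow 7.4 and 7.4.1.E, that table will contain Cohort I events only, without saying so.

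**Working it through.** **Step 1: reproduce the plan's own figure.** The last study visit is post-randomisation week 18 (section 6), and notification runs for 12 further weeks (7.4.1.E). 18 + 12 = 30, which matches the stated week 30. The Cohort II window is therefore week 0 to week 30, a length of 30 weeks.

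**Step 2: place the switch on the same time axis.** Take randomisation as week 0. Section 5.2.3 puts the change at week −6; the Summary footnote puts it at week −6 or earlier. Both put it after consent.

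**Step 3: size of the gap for one participant.**
- Uncovered time = window start − switch = 0 − (−6) = 6 weeks, as a minimum.
- Time from switch to week 30 = 6 + 30 = 36 weeks, as a minimum.
- Share covered for a switch exactly six weeks ahead = 30/36, about 83%. An earlier switch lowers this share.
- Section 6.1.1 places Cohort II screening in the 2 weeks before randomisation. So 6 − 2 = 4 of the uncovered weeks come before the screening window, and up to 2 fall within it.

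**Step 4: total size.** With n participants switching for entry, the uncovered time is at least 6 × n participant-weeks. The documents do not give n, and it could be zero. Participants already on raltegravir go straight to screening, and those who join on their current regimen make no study-driven change (5.2.3).

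**Step 5: follow an SAE in the gap through the rules.**

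| Course after an SAE in the gap | Within the Cohort II window in 7.4.1.E? |
|---|---|
| Recovers, tolerates the regimen, is randomised | No: the event came before week 0 |
| Does not tolerate the regimen, is not randomised | No: there is no week 0, so the window never opens |

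**Step 6: compare the reporting texts for Cohort II before randomisation.**

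| Text | SAEs | Grade 3/4 events |
|---|---|---|
| 7.4.1.E, general sentence | From recruitment, a term not defined there | Not addressed |
| 7.4.1.E, Cohort II sentence | Not covered | Not addressed |
| 7.4, pre-randomisation bullet | Not addressed | Cohort I only |
| 6.3 and SAP 2.3 | Collected, no cohort limit | Collected, no cohort limit |

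Section 6.3 and SAP 2.3 would capture the event, but they give no start point for Cohort II and do not displace the explicit start in 7.4.1.E.

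**The case against.** The best defence is that the documents treat pre-randomisation safety collection as a Cohort I matter on purpose. In 7.4.1.E the sentence about recruitment is followed at once by the two cohort sentences that explain it, and the Cohort II visit table has no enrolment visit. Section 7.4 and SAP section 3 likewise tie pre-randomisation data to Cohort I. On that reading the general sentence in 6.3 and SAP 2.3 is only loosely worded. The amendment log is consistent with this: for the addition of Cohort II it lists 7.4 and 7.4.1.E as updated but not 6.3. That is an inference, not a statement in the plan. This defence stands against calling 7.4.1.E flatly self-contradictory. It does not remove the gap, because a deliberate start at randomisation still excludes a change of drug made for the study.

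Several stronger readings might be inferred, and the documents do not support them:

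- **That anyone harmed before randomisation drops out of the record.** Cohort I SAEs are notified from enrolment. The rule in section 3.1 that no further data are collected applies to Cohort I participants who become ineligible and to people in either cohort who withdraw consent. It does not mention a Cohort II participant who is not randomised for another reason. Section 6.1.1 requires a register with the reason for non-randomisation, and SAP 4.2 presents those reasons. A register entry is not SAE reporting, however: it carries no grading, causality assessment or 24-hour notice.
- **That every SAE in the gap would otherwise be expedited.** The 7- and 15-day timelines in 7.5 apply to SUSARs, so the event must be at least possibly related and unexpected.
- **That study-supplied drug is being given outside safety reporting.** The suggested Cohort II dispensing in 5.6.1 and 5.6.2 starts at the randomisation visit, and 5.1 describes raltegravir as a marketed product. Study supply in the gap is not shown. The change is still made for study entry, after consent, to a listed product.
- **That the plan already implies reporting from consent.** None of the texts names consent. Cohort I itself starts at enrolment, after screening.

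**Conclusion.** The concern holds for a defined group: Cohort II participants who change to raltegravir in order to enter the study. For each of them at least six weeks after the change lie outside the Cohort II SAE rule, and a serious reaction that prevents randomisation would never become notifiable under it. Section 6.3 and SAP 2.3 point the other way, so a site cannot tell from the documents what to report.

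This rests on two assumptions: that sites follow the cohort-specific sentence in 7.4.1.E over the general one, and that switches occur at the recommended time. The number of people affected is unknown and may be small. Sample size, the primary analysis and the comparison of adverse events between arms are unaffected, because the arms are compared on data from randomisation onward. It is a safety-reporting gap that should be closed, not a threat to the trial's efficacy conclusion.

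**What to change.** Amend 7.4.1.E, and the matching bullet in 7.4, so that for Cohort II participants who change ART for study entry, SAE reporting starts no later than the date of that change. Start grade 3/4 reporting at the same point, in line with 6.3 and SAP 2.3. Then reconcile 7.4, 7.4.1.E, 6.3 and SAP 2.3 so that each states the start point by cohort.

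Starting at the switch is enough to close the gap. Starting at consent for all of Cohort II would go further than the gap requires and would give Cohort II an earlier trigger than Cohort I.

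The cost is a wording amendment and a few extra copies of existing forms. No dose, visit, schedule or clinical rule changes.
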